### **Abbreviations**

*This page is optional. The list below includes some common abbreviations. However, this list should be customized for each protocol (i.e., abbreviations not used should be removed and new abbreviations used should be added to this list).*

AE	Adverse Event
IRB	Institutional Review Board
PI	Principal Investigator
US	United States

## 1.0 Background & Rationale

Polypectomy is an important aspect of colonoscopy for colorectal cancer prevention. Large sessile polyps ( $\geq 20$  mm in any dimension) are particularly challenging to remove. Endoscopic mucosal resection (EMR) is an effective therapy for patients with large laterally spreading colon neoplasms measuring greater than 20 mm^2. Main complications of endoscopic resection include bleeding, perforation, transmural injury and recurrence. Our anecdotal observation is that most patients with large colorectal lesions complain of pain immediately after polypectomy when using epinephrine.

Epinephrine is sometimes used as an additive to submucosal injection fluid primarily to reduce immediate (intra-procedural) hemorrhage. The submucosal injection generally consists of non-allergenic viscous solution to raise the polyp away from the submucosa thereby reducing the chance of submucosal injury and perforation. Adding epinephrine to this solution is generally accepted and left to endoscopist discretion. We hypothesize that the complaint of pain in patients with polypectomy of colorectal lesions might be due to the use of epinephrine. Epinephrine reduces the propensity for immediate bleeding by contracting the blood vessels in the surrounding area where it's injected, causing a degree of ischemia. Any relative ischemia might be the cause of the patients' pain.

## 2.0 Objective

To identify if epinephrine use during EMR will result in a change in patient pain perception

## 3.0 Outcome Measures/Endpoints

### **3.1 Primary Outcome Measure**

The primary outcome measure is the mean of the two pain scores assessed on a visual analog scale (VAS, 10 cm vertical line, appendix 1) at 30 minutes and one hour after colonoscopy.

### **3.2 Secondary Outcome Measures**

We will also collect information on the ease of polypectomy (Sydney resection quotient, *en bloc* resection, quality of mound) and frequency of immediate bleeding among both groups.

## **4.0 Eligibility Criteria**

### **4.1 Inclusion Criteria**

1. Patients aged 18 years and over
2. Patients scheduled for treatment of large ( $\geq 20$  mm) colorectal polyps
3. Able to sign informed consent

### **4.2 Exclusion Criteria**

1. Patients previously enrolled in the study
2. Pedunculated polyps
3. Polyps not amenable to endoscopic resection
4. Patients allergic or sensitive to epinephrine

5. Patients with coronary artery disease who have had a myocardial infarction in the past year, or had coronary stenting in the past year, or had angina in the past year.
6. Patients electing anesthesia other than monitored anesthesia care with propofol (MAC) for colonoscopy

[figure not shown]
## **5.0 Study Design**

All patients scheduled for the resection of a colorectal polyp  $\geq 20$  mm in diameter under MAC with propofol will be approached and explained the purpose of the study. If the patient is eligible, and willing to participate in the study and signs an informed consent, patient will be enrolled in the study. Randomization will be performed after [name] measures the polyp as  $\geq 20$  mm in diameter and decides on employing EMR for polypectomy.

If EMR is not employed, the patient will not be randomized and will be excluded from the study. Randomization is computer generated using a 1:1 ratio for the two arms in the study.

Patients in the epinephrine arm will receive a submucosal injection of hetastarch and indigo carmine dye with diluted epinephrine (1:200,000, 5 $\mu$ g/ml). Patients in the no epinephrine arm will receive submucosal injection of hetastarch and indigo carmine dye but no epinephrine. Submucosal injection will be prepared by a registered nurse in the technicians' area away from the endoscopy room and the endoscopist will not be aware of the randomization. The endoscopist will administer the submucosal fluid. The total volume of injected fluid will be

determined by the lesion and the need for fluid volume to achieve adequate lift before snare resection, and will not exceed 100 ml.

## 6.0 Enrollment/Randomization

The subject will be randomized to one of the 2 arms – Epinephrine arm and non-epinephrine arm after the PI inspects the polyp for EMR potential. The research coordinator at this point will break the randomization by opening a sealed envelope. The PI will be blinded to the injection solution throughout the study.

## 7.0 Reportable Events

All adverse events meeting prompt reporting criteria will be reported to the IRB within 5 business days of the study team becoming aware of the event. An adverse event for this study is

defined as any event assessed by the PI, or appropriately trained and qualified designee, as (1) unexpected, (2) related or possibly related to study participation, AND (3) suggesting that the research places subjects or others at greater risk of harm than was previously known. The period for assessing AE's will be from the point of injecting submucosal fluid till the patient is discharged.

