## **8.0 Data Safety Monitoring**

The PI, [name] has a large practice of resecting large polyps and we hope to recruit the 20 patients as quickly as possible. Although this is a randomized trial, both arms of the study are currently commonly used in clinical practice and both are within the standard of care. [name] also uses both approaches in his practice. The use of epinephrine (1:200,000 as generally used in colon polypectomy) does not add significantly to the cost of the procedure and doesn't raise important safety issues. All safety precautions for large polyp resection will be followed. [name] will monitor adverse events including delayed hemorrhage, post-polypectomy syndrome and perforations.

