## **11.0 Statistical Data Management**

Primary data will be collected via paper charts and stored electronically on the S-drive located on IUSM Gastroenterology servers. Access will be limited and password controlled. Data on S-drive is backed up continuously and copies transferred to secure storage every 30 days. We will use Microsoft Excel for data entry and storage. Paper charts will be stored in the administration area away from the endoscopy suite. Charts will be stored for a period of 5 years from the end of the study recruitment. As part of quality control, Excel file will be checked for data entry errors at recruitment of 10 patients.

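### Adverse event assessment ends at discharge, yet delayed hemorrhage is named for monitoring and no later window or data source is given

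*Combined protocol and SAP*

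**What the plan says.** Section 7.0 (Reportable Events) fixes the period for safety assessment: "The period for assessing AE's will be from the point of injecting submucosal fluid till the patient is discharged". The same section defines what counts as an adverse event in this study, by three conditions that must all be met in the judgment of the PI or a qualified designee: "1) unexpected, (2) related or possibly related to study participation, AND (3) suggesting that the research places subjects or others at greater risk" than was known before. It opens with a reporting rule: "All adverse events meeting prompt reporting criteria will be reported to the IRB within 5 business days".

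Section 8.0 (Data Safety Monitoring) says that a named person, apparently the PI, "will monitor adverse events including delayed hemorrhage, post-polypectomy syndrome and perforations". It attaches no time limit, follow-up contact or record source to that commitment.

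Section 1.0 gives the clinical context. Epinephrine is added to the injection fluid "primarily to reduce immediate (intra-procedural) hemorrhage", and "Main complications of endoscopic resection include bleeding, perforation, transmural injury and recurrence". The only bleeding outcome, in section 3.2, is immediate bleeding, which section 10.0 compares between arms with a chi-square test.

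**The concern.** Sections 7.0 and 8.0 both speak of adverse events, but they do not fit together. One closes assessment when the patient leaves. The other undertakes to monitor complications that can appear later. Study staff who follow the only stated window would not record a hemorrhage that starts after discharge.

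Bleeding is the complication most closely tied to the randomized difference, because reducing it is the stated purpose of epinephrine. If the record by arm stops at discharge, a reader of the results cannot tell whether there were no delayed hemorrhages or whether nobody looked.

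The definition adds a second uncertainty. If an event must be unexpected and must point to new risk before it is an adverse event at all, the complications that section 1.0 already lists would ordinarily drop out, although section 8.0 calls events of this kind adverse events.

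**Working it through.** The plan gives no figure for this point, so the check is a comparison of its sections, followed by a simple statement of scale.

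1. **What delayed means.** The documents do not define it. Section 1.0 equates immediate with intra-procedural, so delayed hemorrhage can be read as bleeding after the procedure has ended.

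2. **Which events the window covers.** On that reading there are two cases:
   - Onset after the procedure but before discharge: inside the section 7.0 window.
   - Onset after discharge: outside it.

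   The same split applies to post-polypectomy syndrome and to a perforation recognized late.

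3. **Whether another section supplies a later window or source.**
   - Section 3.1: pain is scored "at 30 minutes and one hour after colonoscopy". The one-hour score is the last timed assessment in the plan.
   - Section 3.2: the ease-of-polypectomy measures and immediate bleeding, with nothing after discharge.
   - Sections 5.0 and 6.0: consent, randomization, injection and blinding, with no follow-up contact.
   - Section 9.0: withdrawal only.
   - Section 10.0: among complications, only immediate bleeding is analyzed.
   - Section 11.0: "Primary data will be collected via paper charts", with no statement on whether the charts cover the time after discharge.

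   None closes the gap. The study schema and one figure are not reproduced in the text available and could not be checked.

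4. **The definition.** Section 7.0 joins its three conditions with AND. Bleeding and perforation are listed in section 1.0 as main complications, so they would ordinarily fail the first condition (unexpected) and the third (new risk). A perforation seen before discharge is inside the time window, so for that event the conflict is with the definition alone. The term unexpected is not defined, which leaves the assessor some room.

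5. **An alternative reading of the definition.** The three conditions may have been meant only as the trigger for prompt reporting to the IRB. That would remove the problem in step 4. It would not remove the one in step 2, because the sentence with the discharge cut-off concerns the assessment of adverse events and not their reporting.

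6. **Scale.** The share of delayed hemorrhages that arise after discharge could be anywhere from 0% to 100% on what the documents give. What can be computed is the effect of one unrecorded patient-event:
   - in an arm of n patients, the recorded proportion falls by 1/n; with the planned n = 10, 1/10 = 10 percentage points;
   - in all 20 patients, 1/20 = 5 percentage points.

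   These figures assume the planned numbers are reached, with 10 in each arm. No event rate is assumed.

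**The case against.** The strongest reply is that this is a silence and not a contradiction. Section 7.0 is headed Reportable Events and begins with prompt reporting, while section 8.0 concerns monitoring and carries no time limit. The two can coexist, and a delayed bleed before discharge is covered in any case. This stands in part: the conflict is confined to events after discharge. For those events, however, the only window in the text excludes them, and section 8.0 offers nothing in its place.

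The point about the definition is weaker. Section 8.0 itself calls perforation and delayed hemorrhage adverse events, and its wording presents the three complications as examples, not as a closed list. The authors probably did not intend to leave known complications uncollected. That is fair, and the definition is therefore a secondary matter of drafting.

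It can also be said that the objective is pain, that both arms are described as standard care, and that the three complications are not listed outcomes. All true, and this limits the importance of the point without reconciling the two sections.

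Finally, the inconsistency could be removed the other way, by stating that monitoring covers only the stay in the unit. That would be coherent, but it would collect less safety information and give up any record of hemorrhage after discharge.

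**Conclusion.** The concern holds. The stated window ends at discharge, section 8.0 names complications that can arise later, and no visible section gives a later window, contact or source. Following the plan as written would leave such events after discharge unrecorded.

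The consequence is limited to the completeness of the safety record. The number of missed events cannot be estimated, and the per-event effect calculated above shows only how coarse proportions are in a trial of this size. The pain endpoint, its test, the sample size and the immediate-bleeding analysis do not depend on this. The point should be fixed, but it does not threaten the trial's main result.

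The conclusion assumes that delayed means after the procedure and that the parts not reproduced (schema, figure, consent pages) contain no follow-up arrangement. The textual conflict over the window is firm. The reading of the definition is less so.

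**What to change.** Reconcile sections 7.0 and 8.0 by a short amendment:

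- State that the three-part test is only the trigger for prompt reporting to the IRB.
- Define adverse events for data collection separately, so that expected events are recorded, including the three complications in section 8.0.
- For those three, set a collection window that extends past discharge, at a time point the investigator chooses, and name medical-record review as the source.
- List the events descriptively by arm, without a significance test.

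The cost is the rewording of two sections and record review for 20 patients, with no new visit or procedure. Record review can miss events treated elsewhere, so a zero count should be reported as none found in the records reviewed. The consent pages were not available here. Whether consent already covers records after discharge should be checked before the change is made.

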## **8.0 Data Safety Monitoring**

The PI, [name] has a large practice of resecting large polyps and we hope to recruit the 20 patients as quickly as possible. Although this is a randomized trial, both arms of the study are currently commonly used in clinical practice and both are within the standard of care. [name] also uses both approaches in his practice. The use of epinephrine (1:200,000 as generally used in colon polypectomy) does not add significantly to the cost of the procedure and doesn't raise important safety issues. All safety precautions for large polyp resection will be followed. [name] will monitor adverse events including delayed hemorrhage, post-polypectomy syndrome and perforations.

## **9.0 Study Withdrawal/Discontinuation**

Any patient who likes to withdraw from the study at any point can do so. The data collected until the patient withdraws consent will be used to maintain data integrity.

## **10.0 Statistical Considerations**

We hope to recruit 10 patients into each arm of the study. Our anecdotal observation is that using epinephrine dramatically increases the post-procedure pain perception of patients. To our

knowledge, there is no literature comparing these two groups with pain outcome measure. The visual analog score is widely used for pain during colonoscopy procedures but there are no relevant publications testing whether epinephrine affects pain after EMR. We calculated that the total sample size of 20 will have 90% power to detect a 50% decrease in mean pain scores at a 2-sided type 1 error rate of 0.05 using a student's t-test (a decrease of mean VAS from 90 with epinephrine to 45 without epinephrine, with a standard deviation of 30 in each group). Sydney resection quotient and quality of mound will be analyzed using Wilcoxon rank sum tests. The proportion of patients who have an en bloc resection and immediate bleeding will be compared using chi-square tests.

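### Should the primary t-test have been adjusted for polyp size, which is known before randomization?

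*Combined protocol and SAP*

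**What the plan says.** Section 3.1 defines a continuous endpoint: "The primary outcome measure is the mean of the two pain scores assessed on a visual analog scale", taken at 30 minutes and one hour. No pre-procedure pain score is listed.

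Section 10.0 states the planning case. A "total sample size of 20 will have 90% power to detect a 50% decrease in mean pain scores", which is spelled out as "a decrease of mean VAS from 90 with epinephrine to 45 without epinephrine", "with a standard deviation of 30 in each group", tested "at a 2-sided type 1 error rate of 0.05 using a student's t-test". The t-test is named only in this power statement. No separate paragraph sets out the primary analysis, so the unadjusted t-test is inferred to be that analysis.

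Section 5.0 places randomization after the step in which the endoscopist "measures the polyp as" at least 20 mm. Allocation is 1:1 and computer generated, and no stratification factor is named there or in Section 6.0. The injected volume is "determined by the lesion and the need for fluid volume to achieve adequate lift before snare resection", with a ceiling of 100 ml. Only one arm's fluid contains epinephrine.

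**The concern.** Polyp size is a true baseline covariate that the trial has to measure anyway. A larger lesion plausibly needs more fluid and more resection and, in one arm, brings more epinephrine, so size might well predict pain. Neither the randomization nor the test takes account of it.

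In a trial of 20 patients, one arm can easily draw the larger polyps. The estimated pain difference would then partly reflect lesion size. If size is strongly prognostic, the unadjusted test also gives up power, in a trial whose planned effect has no literature behind it.

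**Working it through.** **Inputs.** From Section 10.0: n = 10 per arm ("We hope to recruit 10 patients into each arm of the study"), difference 45, SD 30, two-sided alpha 0.05. The within-arm correlation r between polyp size and pain is not in the protocol. It is an assumption, varied from 0 to 0.7.

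**1. The plan's own figure.** The standard error of the difference is 30 × √(2/10) = 13.42, and the noncentrality is 45/13.42 = 3.35. The normal approximation gives Φ(3.35 − 1.96) = 91.8%. The noncentral t with 18 degrees of freedom gives 88.7%. Both lie within 2 points of the stated 90%.

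**2. Size of a chance imbalance.** The between-arm difference in mean size has SD √(2/10) = 0.447, in units of the SD of size.
- P(difference > 0.5 SD, either direction) = 2 × [1 − Φ(0.5/0.447)] = 26%.
- P(difference > 1 SD) = 2.5%.
- A 0.5 SD imbalance moves the pain difference by 0.5 × r × 30, which is 4.5 points at r = 0.3, 7.5 at r = 0.5 and 10.5 at r = 0.7.

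The 7.5-point shift is 7.5/13.42 = 0.56 of a standard error and one sixth of the planned 45. Significance needs an observed difference of 2.10 × 13.42 = 28.2. At r = 0.5, imbalance alone would have to reach 28.2/15 = 1.88 SD of size to produce that, with probability about 0.00003.

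**3. What adjustment costs.** With normally distributed size, estimating the slope multiplies the variance of the treatment difference on average by 1 + 1/(18 − 2) = 1.0625 (simulated: 1.063). It also uses one degree of freedom. The benefit is a factor of 1 − r². On variance alone the two balance when 1 − r² = 1/1.0625, so r = 0.24. Allowing for the lost degree of freedom, the break-even in power is about 0.25 to 0.27.

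**4. Power of the adjusted analysis** (17 degrees of freedom, residual SD 30√(1 − r²), averaged over chance imbalance), against 88.7% unadjusted:

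| r | Power, adjusted | Expected 95% CI half-width (unadjusted 28.2) |
|---|---|---|
| 0 | 86.6% | 29.1 |
| 0.2 | 87.9% | 28.6 |
| 0.3 | 89.5% | 27.8 |
| 0.4 | 91.6% | 26.7 |
| 0.5 | 94.2% | 25.2 |
| 0.7 | 98.9% | 20.8 |

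**5. The dose pathway.** If larger lesions hurt more because more epinephrine is injected, the relation exists in one arm only. Suppose the correlation is r in the epinephrine arm and 0 in the other, with SD 30 in both. A common slope then picks up a pooled within-arm correlation of (r + 0)/2. A correlation of 0.5 in the epinephrine arm counts as 0.25, with adjusted power of about 88.6% against 88.7%. Reaching 0.27 would need 2 × 0.27 = 0.54 in that arm. On this mechanism, a common-slope adjustment gains nothing unless the association is strong.

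**The case for a change.** The strongest argument for adjustment is conditional. Type I error is controlled over all randomizations, but only one will be analyzed. In simulation at r = 0.5, among trials with an imbalance above 0.5 SD, the t-test rejects a true null 9.6% of the time (6.7% at r = 0.3). If the epinephrine arm draws the smaller polyps by that margin, power for the full planned effect falls to about 69% (79% at r = 0.3). The trade is also lopsided: at worst 88.7 − 86.6 = 2.1 points are lost, while 94.2 − 88.7 = 5.5 are gained at r = 0.5. If the true difference were 30, power would be 56.2% unadjusted against 65.8% adjusted at r = 0.5 (53.7% at r = 0). An adjustment chosen after seeing an imbalance would be post hoc.

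These figures are correct given r, and r is what is missing. The conditional excess is offset in the remaining randomizations: at r = 0.5 their rejection rate is (5.0 − 0.264 × 9.6)/0.736 = 3.4%, so the test is neither invalid nor biased on average. Nothing in the protocol shows that size predicts pain. Section 1.0 hypothesizes ischemia from epinephrine and does not mention size. Section 5.0 ties volume to the lesion and to adequate lift, not to size alone.

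The gains also assume a normal outcome linear in a normal covariate. Size is cut off at 20 mm, and one very large lesion could dominate a slope fitted in 20 patients. What stands is that a prespecified size-adjusted analysis would be legitimate. As a sensitivity analysis it would leave the primary conclusion unchanged.

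**Conclusion.** The concern does not hold. Size is known before allocation, no stratification is stated and the only test named is unadjusted, but none of this makes the analysis wrong. The t-test is valid, and the stated power reproduces to within 2 points.

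For the planned effect, adjustment would change power by between −2.1 points (r = 0) and +5.5 points (r = 0.5). The sign turns on whether r exceeds about 0.25 to 0.27, which the protocol gives no means to judge. Under an epinephrine-only pathway with equal SDs, the threshold in that arm is about twice as high. Reasonable statisticians would differ on whether to spend a degree of freedom on a covariate of unknown prognostic value with 20 patients.

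These figures rest on n = 10 per arm, SD 30, normality, a linear relation and, except in the epinephrine-only case, a common slope. They also take the test in the power statement to be the primary analysis.
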